### 1.2.2 Radium-223

Radium-223 (Bayer Pharmaceuticals, NJ) is a calcium mimetic which localizes to bone at areas with increased bone turnover. Radium-223 decays via a chain of short-lived daughter nuclides to lead, producing four alpha-particles [13]. The high energy of alpha particle induces effective double stranded DNA breaks with short range of less than 100  $\mu\text{m}$ , minimizing myelosuppression and causing limited effects on normal tissue.

Radium-223 was approved by the US FDA on May 15, 2013 based on the interim results from a Phase III randomized trial, the ALSYMPCA study (Alpharadin in the treatment of patients with symptomatic bone metastases in castration-resistant prostate cancer). In this trial, 921 patients who had received, were not eligible to receive, or declined docetaxel were randomly assigned in a 2:1 ratio to receive six injections of radium-223 (at a dose of 50 kBq per kilogram of body weight intravenously (55 kBq/kg after implementation of NIST standard update) every 4 weeks or matching placebo. At the interim analysis, which involved 809 patients, radium-223, as compared with placebo, significantly improved overall survival (median, 14.0 months vs. 11.2 months; HR=0.70; 95% CI, 0.55 to 0.88; two-sided P=0.002). The updated analysis involving 921 patients confirmed the radium-223 survival benefit (median, 14.9 months vs. 11.3 months; HR=0.70; 95% CI, 0.58 to 0.83; P<0.001). The rate of AEs was consistently lower in the radium-223 group than in the placebo group for all AEs (93% vs. 96%), grade 3 or 4 AEs (56% vs.

62%), and serious AEs (47% vs. 60%). There were no clinically meaningful differences in the frequency of grade 3 and 4 hematologic AEs. Only one patient developed grade 3 febrile neutropenia in the radium-223 group. For serious AEs that occurred in at least 5% of patients in the radium-223 group or the placebo group, the respective frequencies were as follows: disease progression (11% and 12%), bone pain (10% and 16%), anemia (8% and 9%), and spinal cord compression (4% and 5%). Also a significantly higher percentage of patients who received radium-223 had a meaningful improvement in the quality of life according to the Functional Assessment of Cancer Therapy-Prostate (FACT-P) total score during the period of study-drug administration (25% vs. 16%,  $P=0.02$ ).

## **2.0 OBJECTIVES**

### **2.1 Primary Objective**

- To determine whether radium-223 in combination with sipuleucel-T enhances immune response to sipuleucel-T measured by peripheral PA2024-specific T-cell proliferation compared with sipuleucel-T alone in men asymptomatic or minimally symptomatic bone-metastatic CRPC

### **2.2 Secondary Objectives**

#### **2.2.1 Secondary Immune Objectives**

- To evaluate peripheral antigen-specific T-cell proliferation over time.
- To evaluate peripheral antigen specific T-cell activation to sipuleucel-T over time.
- To evaluate antigen specific antibody response to sipuleucel-T over time.
- To evaluate the sipuleucel-T product immune parameters.

#### **2.2.2 Secondary Clinical Objectives**

- To investigate safety of combined use of radium-223 and sipuleucel-T.
- To evaluate PSA50 response (at least a 50% decline in PSA)
- To evaluate time to radiographic or clinical progression.

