## **3.0 STUDY DESIGN**

This is a randomized study designed to assess the antigen-specific immune response of sipuleucel-T with or without radium-223.

Eligible subjects will be registered and randomly assigned in a 1:1 ratio to receive sipuleucel-T and radium-223 or sipuleucel-T alone;

Version 4.0 Date: 08/21/2020

NCT02463799

The values for radium-223 in this protocol has been revised as per the US NIST standardization update (agreed on 17 Mar 2015)

Arm 1: 6 infusions of radium-223 with 3 infusions of sipuleucel-T starting after second dose of radium-223

Arm 2: 3 infusions of sipuleucel-T alone

Subjects in both arms will undergo a standard 1.5 to 2.0 blood volume leukapheresis, followed approximately 3 days later by an IV infusion of sipuleucel-T. This process will occur a total of 3 times at approximately 2-week intervals. Subjects in Arm 1 will receive a total of 6 infusions of radium-223 at IV dose of 50 kBq/kg (55 kBq/kg after implementation of the NIST update) at 4-week interval.

All participants are allowed to receive the best supportive care which includes secondary hormonal manipulation (including flutamide, bicalutamide or nilutamide-but not abiraterone or enzalutamide) as required. No chemotherapy, external-beam radiation, or other radionuclides are allowed while on active treatment but are permitted after completion of active treatment. Glucocorticoid-containing treatments should be minimized to less than the equivalent dose of prednisone 10mg daily if feasible for the 3 months following sipuleucel-T therapy. All patients continue medical or surgical castration during treatment.

[figure not shown]
**Research visits** will be scheduled at screening, at each radium-223 infusion, prior to each leukapheresis (preleukapheresis visit), and week 32, 45 and 58 for Arm 1 (radium-223 and sipuleucel-T combination arm) and at screening, prior to each leukapheresis (preleukapheresis visit), and week 6, 10, 14, 26, 39, and 52 for Arm 2 (sipuleucel-T alone arm) for physical examinations, vital signs, ECOG performance status, adverse event (AE) monitoring, anticancer therapies, first opioid use for cancer-related pain, and laboratory tests. Serum PSA will be assessed at baseline, and week 16, 32, 45, and 58 for Arm 1 and at baseline, and week 10, 26, 39, and 52 for Arm 2. There is a  $\pm 7$  day window for each visit to accommodate holidays, vacations, etc.

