### 8.3 Populations for Analyses

The immune response population will be defined as subjects who receive 3 infusions of sipuleucel-T and 2 infusions of radium-223. Analysis of immune response endpoints, including

Version 4.0 Date: 08/21/2020

NCT02463799

The values for radium-223 in this protocol has been revised as per the US NIST standardization update (agreed on 17 Mar 2015)

the primary endpoint, will be performed using this population. This population will also be used to perform supplementary analyses of non-immune response efficacy endpoints.

The safety population will include all subjects who receive at least 1 leukapheresis procedure or receive at least 1 dose of radium-223. All safety variables (e.g., AEs, laboratory data, and vital sign data) will be analyzed based on the safety population.

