#### **8.6.4 Safety Analyses**

Safety data will be summarized descriptively in aggregate within the safety population. No formal statistical testing is planned for the safety data.

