##### **8.6.4.1 Adverse Events**

Adverse events will be summarized and listed by the Medical Dictionary for Regulatory Activities (MedDRA) terms, by preferred term within each system organ class. Summary tables will include all AEs reported from the first radium-223 infusion.

Summaries to be produced include the following:

- Incidence within system organ class (MedDRA).
- Incidence by decreasing frequency.
- Incidence by NCI CTCAE severity grade, by decreasing frequency.
- Incidence of Grade  $\geq 3$  AEs, by decreasing frequency.
- Incidence of SAEs.
- Incidence of AEs within 1 day of infusion.
- Incidence of AEs that resulted in premature discontinuation of study treatments.

Adverse events that occur multiple times for a subject will be counted only once per subject in incidence summary tables. In tables that enumerate AEs by severity, only the greatest severity for an AE occurring multiple times for a subject will be counted.

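### Adverse events run as one period from the first radium-223 infusion, so the planned tables do not separate Arm 1's radium-only lead-in (nominally 6 weeks) from combined exposure

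*Combined protocol and SAP*

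**What the plan says.** The safety objective in section 2.2.2 is "To investigate safety of combined use of radium-223 and sipuleucel-T". Section 3.0 defines Arm 1 as "6 infusions of radium-223 with 3 infusions of sipuleucel-T starting after second dose of radium-223". The Arm 1 schedule in section 6.1 puts radium-223 at weeks 0, 4, 8, 12, 16 and 20 and the first sipuleucel-T infusion at week 6. Its footnote c lets that infusion fall anywhere between radium doses 2 and 3.

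The analysis text is brief:

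- Section 8.6.4: "Safety data will be summarized descriptively in aggregate within the safety population". No arm and no period is named, and no formal test is planned.
- Section 8.6.4.1, start of counting: "Summary tables will include all AEs reported from the first radium-223 infusion".
- Section 8.6.4.1, counting rules: "Adverse events that occur multiple times for a subject will be counted only once per subject in incidence summary tables", and in the severity tables "only the greatest severity for an AE occurring multiple times for a subject will be counted".
- Section 8.6.4.1, the only listed summary tied to timing: "Incidence of AEs within 1 day of infusion". It does not say which product was infused.
- Section 8.3, safety population: "all subjects who receive at least 1 leukapheresis procedure or receive at least 1 dose of radium-223". This rightly keeps Arm 1 men who had radium-223 but never reached leukapheresis.

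**The concern.** An Arm 1 man spends several weeks on radium-223 alone before he meets sipuleucel-T. Events that begin in those weeks cannot be effects of giving the two agents together, yet they enter the same rows as events that begin later. None of the seven listed summaries separates the two periods. Relatedness does not help, because section 7.2 grades it against study treatment as a whole and not agent by agent.

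The counting rule removes further information. A man with grade 2 fatigue in week 3 and again in week 9 contributes one event, and nothing in the table shows that it recurred under both agents. A column for each arm would not cure this, because the Arm 1 column would still merge the two exposures.

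The same sentence leaves Arm 2 without a start date, since those men receive no radium-223. The intention is presumably to tabulate them too, but the rule does not say from when.

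At stake is how clearly the planned tables answer the combined-use objective. The primary endpoint and the test on it are untouched.

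**Working it through.** **1. Length of the lead-in.** Each Arm 1 immune visit has a study week (section 6.1, schedule a) and a stated number of weeks after the first sipuleucel-T infusion (footnote d). The difference is the lead-in:

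12−6 = 16−10 = 20−14 = 32−26 = 45−39 = 58−52 = 6 weeks.

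The week-6 start is therefore reproduced at all six post-baseline visits. Footnote c allows 4 to 8 weeks, before the ±7-day visit window. Leukapheresis comes about 3 days before infusion (section 5.2.4), so a cut at the first leukapheresis falls about 3 days earlier.

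**2. Share of observation.** This depends on which collection rule governs.

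| | All-cause collection to week 20 (6.6.1) | Collection throughout (7.3; AE row of the schedules) |
|---|---|---|
| Lead-in share, start at week 6 | 6/20 = 30% | 6/58 = 10% |
| Start at week 4 | 4/20 = 20% | 4/(4+52) = 7% |
| Start at week 8 | 8/20 = 40% | 8/(8+52) = 13% |
| Weeks observed after first sipuleucel-T, Arm 1 (week-6 start) | 20−6 = 14 | 58−6 = 52 |
| Same, Arm 2 (first infusion at week 0) | 20 | 52 |

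Under 6.6.1, new treatment-related events are still recorded after week 20. The left column therefore describes all-cause events only.

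**3. Illustration of first onsets.** The documents give no event rates for this regimen, so this step is an assumption. With a constant hazard, incidence p over a window of W weeks and a lead-in of L weeks, the share of affected men whose first event falls in the lead-in is

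S = [1 − (1−p)^(L/W)] / p.

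For p = 0.5, L = 6, W = 20: (1 − 0.5^0.3)/0.5 = 0.188/0.5 = 0.375.

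| p | L=4, W=20 | L=6, W=20 | L=8, W=20 | L=6, W=58 |
|---|---|---|---|---|
| 0.2 | 22% | 32% | 43% | 11% |
| 0.5 | 26% | 38% | 48% | 14% |
| 0.8 | 34% | 48% | 59% | 19% |

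In the last column p is the 58-week incidence. Constant hazard is a poor description of typical sipuleucel-T reactions: section 1.2.1 says most of the common ones came within a day of infusion. For those terms the lead-in share would be smaller.

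**4. Does another planned display separate the periods?** Laboratory values (8.6.4.2) and vital signs (8.6.4.3) are summarised by time point, so blood counts are resolved in time. Adverse events are also listed individually. No listed adverse event summary is split by onset.

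**The case against.** The best defence is that the lead-in belongs to the regimen. Arm 1 is a sequence that begins with radium-223, section 8.1 calls it sequential administration, and counting from first dose is ordinary practice. Keeping every dosed man in the safety population is also correct. This stands: the from-first-dose table is not an error and should stay. What the defence does not supply is a display of events under exposure to both agents.

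A reader might infer three stronger things that the documents do not support.

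- *That the trial is unable to describe safety under combined exposure.* Onset and infusion dates would allow the split later, the list of summaries is not said to be exhaustive, and laboratory data are already shown over time. The limit lies in the planned tables, not in the data.
- *That the effect of radium-223 on the tolerability of sipuleucel-T is a stated objective.* Section 2.2.2 names safety of combined use without a comparison, and section 8.6.4 plans no safety test. Nor does section 8.6.4.1 label its tables as combination safety; they are simply the only adverse event tables available for that objective.
- *That the arms are observed for unequal times after sipuleucel-T.* This holds for all-cause events under section 6.6.1. It does not hold under section 7.3 and the schedule, where both arms have 52 weeks.

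A further objection concerns the remedy. A table restricted to men who began leukapheresis conditions on something that happens after randomization. Arm 2 men enter the safety population only through leukapheresis, so the restriction can remove Arm 1 men only, including any stopped by radium-223 toxicity. With about 15 per arm, one man is 1/15, or about 7 percentage points. This also stands, and it rules out making the restricted table the main display.

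**Conclusion.** The point holds as a cheap improvement to sections 8.6.4 and 8.6.4.1. As planned, the adverse event tables merge a radium-only lead-in of nominally 6 weeks (4 to 8 allowed) with the period of exposure to both agents. They can hide a later event of the same term and of equal or lower grade, and they define no start for Arm 2.

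The 6 weeks are firm. The share is conditional: 30% (20% to 40%) of a 20-week all-cause window, or about 10% if collection runs to week 58. The first-onset shares of 32% to 48% rest on a constant hazard and the 20-week window together, and the comparison of 14 with 20 weeks rests on that window. None of these is an estimate of what the trial will observe.

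**What to change.** In sections 8.6.4 and 8.6.4.1:

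1. Keep the overall table for the full safety population and state that it is shown by arm. Start it at the first radium-223 infusion in Arm 1 and the first leukapheresis in Arm 2. Use it for the comparison of whole regimens.
2. Add a descriptive by-arm table split by date of onset, counting each term afresh in each period:
   - Period 1, Arm 1 only: first radium-223 infusion to just before the first leukapheresis, for all men dosed with radium-223.
   - Period 2, both arms: first leukapheresis to one fixed time after the first sipuleucel-T infusion that all-cause collection covers in both arms. Twelve weeks would do, because a week-8 start leaves 20−8 = 12 weeks under section 6.6.1.
3. Label period 2 as conditional on starting leukapheresis. Beside it, give the number of Arm 1 men who stopped earlier and their reasons. It must not replace the overall table.
4. Reconcile the collection periods in sections 6.6.1 and 7.3 and the schedule, so that the chosen window is known to be covered.

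The cost is some SAP wording and one more set of tables, built from onset, leukapheresis and infusion dates. Treatment, visits and sample size do not change. The one real drawback is the post-randomization denominator in period 2, which item 3 makes visible.

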## **3.0 STUDY DESIGN**

This is a randomized study designed to assess the antigen-specific immune response of sipuleucel-T with or without radium-223.

Eligible subjects will be registered and randomly assigned in a 1:1 ratio to receive sipuleucel-T and radium-223 or sipuleucel-T alone;

Version 4.0 Date: 08/21/2020

NCT02463799

The values for radium-223 in this protocol has been revised as per the US NIST standardization update (agreed on 17 Mar 2015)

Arm 1: 6 infusions of radium-223 with 3 infusions of sipuleucel-T starting after second dose of radium-223

Arm 2: 3 infusions of sipuleucel-T alone

Subjects in both arms will undergo a standard 1.5 to 2.0 blood volume leukapheresis, followed approximately 3 days later by an IV infusion of sipuleucel-T. This process will occur a total of 3 times at approximately 2-week intervals. Subjects in Arm 1 will receive a total of 6 infusions of radium-223 at IV dose of 50 kBq/kg (55 kBq/kg after implementation of the NIST update) at 4-week interval.

All participants are allowed to receive the best supportive care which includes secondary hormonal manipulation (including flutamide, bicalutamide or nilutamide-but not abiraterone or enzalutamide) as required. No chemotherapy, external-beam radiation, or other radionuclides are allowed while on active treatment but are permitted after completion of active treatment. Glucocorticoid-containing treatments should be minimized to less than the equivalent dose of prednisone 10mg daily if feasible for the 3 months following sipuleucel-T therapy. All patients continue medical or surgical castration during treatment.

[figure not shown]
**Research visits** will be scheduled at screening, at each radium-223 infusion, prior to each leukapheresis (preleukapheresis visit), and week 32, 45 and 58 for Arm 1 (radium-223 and sipuleucel-T combination arm) and at screening, prior to each leukapheresis (preleukapheresis visit), and week 6, 10, 14, 26, 39, and 52 for Arm 2 (sipuleucel-T alone arm) for physical examinations, vital signs, ECOG performance status, adverse event (AE) monitoring, anticancer therapies, first opioid use for cancer-related pain, and laboratory tests. Serum PSA will be assessed at baseline, and week 16, 32, 45, and 58 for Arm 1 and at baseline, and week 10, 26, 39, and 52 for Arm 2. There is a  $\pm 7$  day window for each visit to accommodate holidays, vacations, etc.

**Imaging studies** including bone scintigraphy test (bone scan) or Na-F PET or C11 acetate PET and abdomen/pelvis CT or MRI will be obtained at screening and week 16, 32, 45, and 58 for Arm 1 and at screening and week 10, 26, 39, and 52 for Arm 2. After the last study visit, imaging studies will be obtained according to the participating institution's standard and/or at the investigator's discretion.

**Immune monitoring** blood samples will be drawn at screening and at 6, 10, 14, 26, 39, and 52 weeks after the first infusion of sipuleucel-T in both arms. Additional blood samples will be obtained at baseline, first pre-leukapheresis visit (only in Arm 1), and weeks 14 and 52 post the first infusion of sipuleucel-T for exploratory antigen spread assessment.

After last study research visit at week 58, safety, treatment-related AEs, survival status, PSA, first opioid use for cancer-related pain (if applicable), and anticancer therapies will be assessed every 3 months for additional 1 year or until the subject's death.

The study design is illustrated in Figure 1.

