### **Study Design and Duration:**

This is a randomized study designed to assess the antigen-specific immune response of sipuleucel-T when administered with or without radium-223.

Eligible subjects will be registered and randomly assigned in a 1:1 ratio to receive sipuleucel-T and radium-223 or sipuleucel-T alone;

Arm 1: 6 infusions of radium-223 with 3 infusions of sipuleucel-T starting after second dose of radium-223

Arm 2: 3 infusions of sipuleucel-T alone

Subjects in both arms will undergo a standard 1.5 to 2.0 blood volume leukapheresis, followed approximately 3 days later by an IV infusion of sipuleucel-T. This process will occur a total of 3 times at approximately 2-week intervals. Subjects in Arm 1 will receive a total of 6 infusions of radium-223 at IV dose of 50 kBq/kg (55 kBq/kg after implementation of the NIST update) at 4-week interval

**Research visits** will be scheduled at screening, at each radium-223 infusion, prior to each leukapheresis (preleukapheresis visit), and week 32, 45 and 58 for Arm 1 (radium-223 and sipuleucel-T combination arm) and at screening, prior to each leukapheresis (preleukapheresis visit), and week 6, 10, 14, 26, 39, and 52 for Arm 2 (sipuleucel-T alone arm) for physical examinations, vital signs, ECOG performance status, adverse event (AE) monitoring, anticancer therapies, first opioid use for cancer-related pain, and laboratory tests. Serum PSA will be assessed at baseline, and week 16, 32, 45, and 58 for Arm 1 and at baseline, and week 10, 26, 39, and 52 for Arm 2. There is a  $\pm 7$  day window for each visit to accommodate holidays, vacations, etc.

**Imaging studies** including bone scintigraphy test (bone scan) or Na-F PET or C11 acetate PET and abdomen/pelvis CT or MRI will be obtained at screening and week 16, 32, 45, and 58 for Arm 1 and at screening and week 10, 26, 39, and 52 for Arm 2. After the last study visit, imaging studies will be obtained according to the participating institution's standard and/or at the investigator's discretion.

Version 4.0 Date: 08/21/2020

[figure not shown]
NCT02463799

The values for radium-223 in this protocol has been revised as per the US NIST standardization update (agreed on 17 Mar 2015)

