## b. Arm 2: sipuleucel-T alone

	Screen a Im-1	PreL-1 b	Sip-1	PreL-2 b	Sip-2	PreL-3 b	Sip-3	Im-2 c	Im-3 c	Im-4 c	Im-5 c	Im-6 c	Im-7 c	F/U d
Week	Week	0	0	2	2	4	4	6 c	10 c	14 c	26 c	39 c	52 c	
Week														
Informed consent	X													
Registration/	X													
Pathology	X													
Sip-T infusion			X		X		X							
Clinical Assessments														
Medical History	X													
P/E	X	X		X		X								
Vital Signs	X	X	X e	X	X e	X	X e	X	X	X	X	X	X	
ECOG PS	X	X		X		X		X	X	X	X	X	X	
Imagingf	X									X	X	X	X	X g
Safety Assessment														
AEs/SAEs		X	X	X	X	X	X	X	X	X	X	X	X	X h
Medication														
Anticancer Tx	X	X		X		X								X
1 st Opioid use	X	X		X		X								X
Survival Status														
Lab Assessments														
Hematology	X	X		X		X								
Chemistry/ LDH/ magnesium / phosphorus	X	X		X		X								
Testosterone	X													
PSA	X								X		X	X	X	
Coagulation k	X													
Immune Assessments														
Dendreon l	X							X	X	X	X	X	X	
JH Lab j	X									X			X	

Version 4.0 Date: 08/21/2020

NCT02463799

The values for radium-223 in this protocol has been revised as per the US NIST standardization update (agreed on 17 Mar 2015)

Abbreviations: AE = adverse event; A/P = abdomen/pelvis; CT = computed tomography; ECOG = Eastern Cooperative Oncology Group; F/U = follow up visit; Im = Immune assessment visit; JH = Johns Hopkins; MRI = magnetic resonance imaging; PAP = prostatic acid phosphatase; P/E = physical exam; PET = positron emission tomography; Sip = sipuleucel-T infusion visit; PS = performance status; PreL = preleukapheresis visit; PSA = prostatic specific antigen; SAE = serious adverse event; Tx = treatment

- a. All screening procedures must occur within 28 calendar days prior to registration, with the exception of written informed consent, histological documentation of prostate cancer with Gleason grading, and imaging for confirmation of metastatic disease
- b. Applies to all leukapheresis; pre-leukapheresis visits will occur  $\leq 5$  days prior to each leukapheresis
- c. At baseline, week 6, 10, 14, 26, 39, and 52 post-first sipuleucel-T infusion

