### **6.5.2 Physical Examination**

Physical examinations will be performed at the times noted in Table 1 and must be conducted by an appropriately qualified investigator listed on the Form FDA 1572.

The physical examinations conducted at screening and at pre-leukapheresis visits will include a review of the skin, pulmonary, cardiovascular, and neurologic systems, abdomen, and extremities. A review of additional body systems will be at the discretion of the investigator.

For all other visits that call for a physical examination, the body systems reviewed will be at the discretion of the investigator.

Each physical examination will include weight measurement. Height will be measured at screening only.

Abnormal physical examination findings at screening will be considered part of the medical history and will be recorded on the Medical History CRF. Any new or worsening physical examination findings identified after the subject's registration will be considered AEs and will be recorded in the subject's medical record and on the CRF.

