## **6.9 Laboratory Test Assessments**

Version 4.0 Date: 08/21/2020

NCT02463799

The values for radium-223 in this protocol has been revised as per the US NIST standardization update (agreed on 17 Mar 2015)

At the times noted in Table 1, blood samples will be obtained for assessment of the parameters presented in Table 2.

Table 2: Clinical Laboratory Tests

Hematology	Chemistry
hemoglobin	sodium
hematocrit	potassium
platelets	bicarbonate
mean corpuscular volume	chloride
mean corpuscular hemoglobin	lactate dehydrogenase
mean corpuscular hemoglobin concentration	blood urea nitrogen
leukocytes	creatinine
neutrophils	phosphorus
lymphocytes	calcium
monocytes	magnesium
eosinophils	glucose
basophils	albumin
	total protein
	total bilirubin
	alkaline phosphatase
	alanine aminotransferase
	aspartate aminotransferase
Other Assessments	
total testosterone	
prostatic specific antigen	
Coagulation	
prothrombin time	
Partial thromboplastin time	
international normalized ratio	

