## 6.10 Immune Assessments

### 6.10.1 Peripheral Immune Response Assessments

Cellular and humoral immune responses will be assessed from 100 mL blood samples (9x10 mL heparin whole blood tubes and 1x10 mL serum tube) collected at the times noted in the Schedule of Assessments (Table 1).

Immune response assessments will include T-cell activation to PA2024 and PAP using IFN- $\gamma$  ELISPOT assay, T-cell proliferation response to PA2024 and PAP by  $^3\text{H}$ -thymidine uptake, and humoral (IgG and IgM) response to PA2024 and PAP by ELISA.

Version 4.0 Date: 08/21/2020

NCT02463799

The values for radium-223 in this protocol has been revised as per the US NIST standardization update (agreed on 17 Mar 2015)

The following research blood samples should be collected and processed as instructed in Immune Monitoring Requisition Form (Appendix 1):

Ship the specimen as instructed in Immune Monitoring Shipping Instructions (Appendix 2)

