#### Exploratory Objectives:

- Median time to PSA progression based on Prostate Cancer Working Group 2 (PCWG2) criteria [1]:
  - in patients with no PSA decline from baseline as:  $\geq 25\%$  increase from the baseline value and an increase in absolute value of  $\geq 2$  ng/mL, at least 12 weeks from baseline
  - in patients with an initial PSA decline from baseline as:  $\geq 25\%$  increase and an absolute increase of  $\geq 2$  ng/mL above the nadir value, which is confirmed by a second value obtained three or more weeks later
- Median time to ALP progression.
  - in patients with no ALP decline from baseline as:  $\geq 25\%$  increase from the baseline value, at least 12 weeks from baseline
  - in patients with an initial ALP decline from baseline as:  $\geq 25\%$  increase above the nadir value, which is confirmed by a second value obtained three or more weeks later.
- Median time to pain progression defined as use of opioid analgesics for cancer-related pain.
- Median time to occurrence of first skeletal related event (SRE):
  - the use of external beam radiotherapy to relieve skeletal symptoms or the occurrence of new symptomatic pathological bone fractures (vertebral or non-vertebral) or the occurrence of spinal cord compression or a tumor related orthopedic surgical intervention.
- Median time to occurrence of first start of chemotherapy use.

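### The Arm 2 schedule table contradicts Section 3.0 and the synopsis on laboratory tests, examinations and the first scan; if the table is followed, ALP progression cannot be ascertained in Arm 2 on nominal dates

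*Combined protocol and SAP*

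**What the plan says.** **Text.** Section 3.0 schedules Arm 2 research visits at screening, before each leukapheresis, and at "week 6, 10, 14, 26, 39, and 52 for Arm 2 (sipuleucel-T alone arm) for physical examinations, vital signs, ECOG performance status". The sentence, which the synopsis repeats, goes on to list "adverse event (AE) monitoring, anticancer therapies, first opioid use for cancer-related pain, and laboratory tests". Imaging in both places is "at screening and week 10, 26, 39, and 52 for Arm 2". PSA has its own sentence, with Arm 2 values at baseline and weeks 10, 26, 39 and 52.

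**Table.** The second table in Section 6.1, headed "Arm 2: sipuleucel-T alone", marks physical examination, haematology and chemistry at screening and at the pre-leukapheresis visits of weeks 0, 2 and 4, and nowhere later. Anticancer-therapy and opioid review have the same marks plus follow-up. Imaging is marked at screening, weeks 14, 26, 39 and 52, and follow-up; week 10 is blank.

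**Which one governs.** Section 6.9 reads: "At the times noted in Table 1, blood samples will be obtained for assessment of the parameters presented in Table 2". Section 6.5.2 reads: "Physical examinations will be performed at the times noted in Table 1". Section 6.10.1 identifies Table 1 as the Schedule of Assessments. No section says whether the text or the table takes precedence.

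**The concern.** Two sites could each follow the protocol and collect different Arm 2 data. Following the table has four consequences.

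- **ALP progression (exploratory).** ALP is measured only within the chemistry panel of Section 6.9, Table 2. With no chemistry after week 4, the definition in Section 8.5.2 has nothing to work on in Arm 2.
- **Laboratory safety.** Graded laboratory abnormalities are part of a secondary clinical endpoint (Section 8.5.2), and Section 8.6.4.2 summarises laboratory data to the end of the study. Arm 2 would contribute data to week 4 and Arm 1 to week 58.
- **Haematologic monitoring.** Section 8.7 counts grade 3 or higher cytopenias in groups of 10 patients, 5 from each arm. The Arm 2 half would have no scheduled blood count after week 4.
- **First scan.** Week 14 breaks the alignment with Arm 1 when time is counted from the first sipuleucel-T infusion.

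**Working it through.** The plan gives no figure to reproduce here. The check is a reconciliation of schedules.

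**Step 1: is the table being read correctly?** Each of the Arm 2 rows checked splits into 14 cells, matching the 14 columns. The PSA row falls at weeks 10, 26, 39 and 52 and the immune-sampling row at weeks 6, 10, 14, 26, 39 and 52, both as in the text. Vital signs, ECOG and adverse events also run to week 52. The columns are therefore not shifted; particular rows stop early.

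**Step 2: scheduled haematology and chemistry draws after screening.**

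| Source | Weeks | Draws | At week 12 or later |
|---|---|---|---|
| Arm 1 table | 0, 4, 6, 8, 8, 10, 12, 16, 20, 32, 45, 58 | 12 | 6 (12, 16, 20, 32, 45, 58) |
| Arm 2 table | 0, 2, 4 | 3 | 0 |
| Arm 2 text | 0, 2, 4, 6, 10, 14, 26, 39, 52 | 9 | 4 (14, 26, 39, 52) |

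The Arm 1 total is 6 radium-223 visits + 3 pre-leukapheresis visits + 3 later visits = 12. Two of these share nominal week 8, so there are 11 distinct weeks. The Arm 2 text total is 3 pre-leukapheresis visits + 6 later visits = 9.

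**Step 3: first ALP rule (no initial decline), Arm 2 table.** The rule requires an "increase from the baseline value, at least 12 weeks from baseline". Section 8.6.4.2 takes laboratory baseline as the last value on or before randomization, and screening may be up to 28 days before registration. The longest span is 4 weeks (last draw) + 4 weeks (oldest screening sample) = 8 weeks. With the +7-day visit window it is 9 weeks. Both fall short of 12. This assumes that week 0 follows registration without delay and that no leukapheresis is rescheduled.

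**Step 4: second ALP rule (initial decline, then a rise confirmed 3 or more weeks later), Arm 2 table.** The earliest sequence is a decline at week 0, a rise at week 2 and confirmation at week 4. The gap is 4 − 2 = 2 weeks, below 3. If the ±7-day windows stretch the draws to weeks 1 and 5, the gap is 5 − 1 = 4 weeks, so the rule becomes possible, but only off the nominal dates.

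**Step 5: scans counted from first sipuleucel-T.** Arm 1, with the first infusion at nominal week 6: 16 − 6 = 10, 32 − 6 = 26, 45 − 6 = 39, 58 − 6 = 52. Arm 2 text: 10, 26, 39, 52. Arm 2 table: 14, 26, 39, 52. Only the first scan differs.

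**The case against.** **The text names no panel.** It says only that laboratory tests are done, and testosterone and coagulation are marked at screening alone in both arms, so the phrase cannot mean every test at every visit. The 9 draws are therefore a reading of the text. That stands as a caveat, but the reading is well supported. PSA is scheduled separately. The Arm 2 table has no clinical laboratory test at all at weeks 6 or 14. The Arm 1 table carries both panels at every visit that the same sentence lists. Section 7.3 expects laboratory evaluation as part of adverse-event assessment at each visit.

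**Section 7.3 may make sites draw blood anyway.** It may, but it orders no named panel, while Section 6.9 defers to the table.

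**The impact is limited.** Much of this is right. ALP progression is exploratory, and Section 8.6.3 assigns its interval-censored method only to the secondary time-to-event endpoints. Safety summaries are descriptive, with no formal test (Section 8.6.4). That interval-censored method copes with unequal scan dates. First opioid use and anticancer therapies must be recorded in any case (Sections 5.5, 6.7.1 and 6.7.2). Section 8.7 sets no observation window per patient, so the number of cytopenias that could be missed cannot be calculated. Visit windows, or repeat tests after a rescheduled leukapheresis (Section 5.2.5), could supply an occasional later value.

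**The fix takes the side of the text.** For laboratory tests and examination it does. The reason is that the protocol's own ALP rule needs chemistry at 12 weeks or later, which the table never schedules. On the scan week the recommendation is neutral.

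**Conclusion.** The concern holds. The text and the Arm 2 table disagree explicitly on physical examination and on the first-scan week (10 against 14). On the best reading of the text they also disagree on haematology and chemistry. Following the table leaves Arm 2 with 3 post-screening draws instead of 9, and none instead of 4 at week 12 or later. Neither ALP rule can then be met on nominal dates, and scheduled laboratory safety data in Arm 2 end at week 4.

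This rests on laboratory tests meaning haematology and chemistry, on week 0 following registration promptly, and on visits keeping to their nominal dates. The primary endpoint and PSA timing are not affected. It is an internal inconsistency that should be corrected, and it does not threaten the main comparison.

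**What to change.** Amend the Arm 2 table so that haematology, chemistry (including ALP), physical examination, anticancer-therapy review and opioid review are marked at the existing visits of weeks 6, 10, 14, 26, 39 and 52. In Section 3.0 and the synopsis, name the panels meant by laboratory tests. State one first-scan week for Arm 2, the same in text and table.

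This gives Arm 2 four nominal ALP dates at week 12 or later, with visits far enough apart for confirmation, so both ALP rules become ascertainable. The remaining difference of 9 against 12 draws comes from Arm 1's additional radium-223 visits.

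The cost is a table amendment, brief examinations, and routine tubes at visits where Section 6.10.1 already calls for 100 mL of blood for immune monitoring. No new visits are needed.
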